#### **4.1.11. Time Since Diagnosis of Schizophrenia**

Time (years) since diagnosis of schizophrenia is calculated as the difference in years from date of diagnosis to date of informed consent.

#### **4.1.12. Handling of Incomplete or Missing Dates**

Incomplete or missing start and end dates will be imputed for adverse events to determine treatment-emergence, for medications/non-drug therapies to determine when the medication/non-drug therapy was taken (i.e., pre-dose, concomitant, or post last dose of IMP), and for date of initial onset of schizophrenia to determine time since onset.

An incomplete date occurs when the exact date an event occurred or ended cannot be obtained from a subject. The database contains data fields for month, day, and year. A date is incomplete if at least one of these three fields is not known.

For the purposes of handling partially reported start and stop dates for an event the following algorithm will be applied:

- Missing start day, but month and year present:  
If the event occurs in the same month and year as the occurrence of IMP, then the start day of the event will be assigned to the day of first dose of IMP (i.e., Day 1).  
Otherwise, the start day will be set to the first day of the month.
- Missing start day and month, but year present:  
If event occurs in the same year as IMP, then the start date of the event will be assigned to Day 1.

Otherwise, the start day and month will be set to 01 January.

- In the unlikely event of a completely missing start date (year not present), the start date will be imputed as Day 1.

- Missing end day, but month and year present:

The day will be set to the last day of the month.

- Missing end day and month, but year present:

The end day and month will be set to the date of study completion.

However, if study completion year is greater than the year of the event, then the day and month will be set to 31 December.

- Missing all components of an end date and the event is not marked as ongoing:

The event will be considered as ‘ongoing’ and will be considered treatment-emergent if the start date is on or after Day 1.

If any imputed start date causes the start date to occur after the end date, the end date will be used for the imputation of the start date. If any imputed end date causes the end date to occur prior to the start date of the event, the start date of the event will be used for the imputation of the end date. If the imputed date is later than the date of study withdrawal, then the date of study withdrawal will be imputed for the date. In subject data listings, start and stop date of events will be displayed as reported on the eCRF (i.e., imputed values will not be listed).

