6. To address ICE of trial or treatment discontinuation with no outcome data collected post discontinuation, the primary analysis of MMRM described above will be followed by pattern mixture model (PMM) approach with varying level of shift parameters for missing values due to discontinuations that are potentially missing not at random (MNAR), including discontinuation due to lack of efficacy or due to adverse events. This will be implemented using delta adjustment imputation method. Further details will be described in the statistical analysis plan (SAP).

The statistical hypothesis testing on the primary endpoint (emraclidine 30 mg QD vs placebo and emraclidine 15 mg QD vs placebo) will be based on the estimated treatment difference from the model at Week 6 and will be tested in a hierarchical order with each at 2-sided alpha level 0.05. The evaluation of other time points will also be derived from the same model.

The number and proportion of responders (ie, participants with 30% reduction from Baseline in the PANSS total score at Week 6 or the last assessment before discontinuation) will be summarized. A logistic regression model, with baseline PANSS as a covariate, will be used to compare the proportion of responders in each active arm with placebo. If expected counts are <5, then a Fisher's Exact test will be used.

The secondary estimand has the following attributes:

1. Treatments as randomized
2. mITT population as the primary population of interest
3. Change from Baseline to Week 6 in CGI-S score as the endpoint of interest
4. The population level summary of interest is the treatment differences estimated based on the least square mean and the corresponding 95% confidence interval from the MMRM model with treatment, visit, and treatment by visit interaction as fixed effect, participant as a random effect, and baseline CGI-S score as a covariate. An unstructured covariance structure will be used for the repeated measures. If the unstructured covariance matrix results in convergence issue, the heterogeneous Toeplitz covariance structure followed by the heterogeneous first-order autoregressive (AR(1)) structure will be used. When a reduced covariance matrix is used, the sandwich variance estimator will be used. The Kenward-Roger approximation will be used to estimate the denominator degrees of freedom.
5. ICEs will be addressed using the same strategies as described above for the primary endpoint.

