4.1.2 Treatment Period

On Day 1 (Baseline), participants will be randomized in a 1:1:1 ratio to the following treatment groups with approximately 124 participants per treatment group:

- Emraclidine 15 mg QD
- Emraclidine 30 mg QD
- Placebo QD

The randomization will be stratified by geographic region with 2 strata: United States or all other countries.

The daily dosing schedule will start on Day 1 with all participants receiving a single daily dose of IMP in the morning.

Participants are to remain in the inpatient facility for the entire duration of the trial (ie, from ICF signing through Week 6/ET); however, beginning at the Week 3 time point, participants who are sufficiently stable (per investigator assessment) may receive day passes for urgent issues. While away from the site, participants must be supervised by hospital/research staff (medical monitor approval for supervision by a family member or caregiver may be obtained). Participants are not permitted to stay away from the inpatient facility overnight; if, in unforeseen circumstances, the participant is unable to return to the facility the same day, the medical monitor should be contacted to discuss continuing participant eligibility. In addition, the participant must agree to submit to testing (ie, urine drug screen and alcohol breathalyzer test) upon return to the site. If the breathalyzer test is positive, the medical monitor should be contacted to determine the continued eligibility of the participant. Participants returning from a day pass who have a positive urine drug screen should be discontinued from the trial. However, if the positive urine drug screen results from use of marijuana (any THC-containing product), prescription, or over-the-counter medications or products that, in the investigator's documented opinion, does not signal a clinical condition that would impact the safety of the participant or interpretation of the trial results, the participant may continue in the trial following consultation and approval by the medical monitor.

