6.6 Intervention After the End of the Trial

Participants who complete through Day 45 of the trial may have the opportunity to receive open-label treatment with emraclidine in an open-label extension trial

(Protocol CVL-231-2003) if available. Participants who are ineligible or elect not to enter the open-label extension trial will resume treatment with available antipsychotic medications at the discretion of and as determined by their physician.

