## 1.2. Sample Size Considerations

A sample size of approximately 93 subjects in each treatment group completing the Week 6 assessments (approximately 279 in total) should provide at least 90% power to detect an effect size of 0.48 in change from Baseline in the Positive and Negative Symptom Score (PANSS) total score at Week 6 between either active treatment group versus placebo at the  $\alpha=0.05$  level. The effect size of 0.48 represents a clinically meaningful effect on symptom reduction based on large scale meta-analysis of historical data from several currently approved antipsychotic medications in common usage ([Leucht et al, 2013](#)). It could be translated into a difference of 7 points versus placebo if the standard deviation of change from baseline is 14.6 points or a difference of 8 points versus placebo if the standard deviation of change from baseline is 16.7 points. Both scenarios of the standard deviation are consistent with historical observations. To account for a discontinuation rate of approximately 25% for a 6-week treatment period (as observed in Trial CVL-231-SCH-001), it is planned to randomize approximately 372 subjects.

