### **3.2.7. Prior Medications, Concomitant Medications and Medications Taken Post Last Dose of IMP**

Prior medications are those medications taken prior to and ended prior to the initiation of IMP. Concomitant medications are those medications taken on or after the initiation of IMP. These medications include those medications started before the initiation of IMP and continuing post Day 1. Medications that start after the last dose of IMP will be classified as taken post last dose and will not be considered as concomitant. These medications will be recorded in the CONCOMITANT MEDICATIONS eCRF.

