## 5.9. Primary Efficacy Analysis

### 5.9.1. Primary Estimand

The key research question for the primary endpoint will be addressed with an estimand based on the following attributes:

1. Treatments: treatments as randomized regardless of the actual treatment received.
2. Target study population of interest: subjects in the mITT population.
3. Endpoint of interest: Change from Baseline to Week 6 in total PANSS score.
4. Population level summary of interest: the treatment differences estimated based on the least square mean and the corresponding 95% confidence interval from the mixed model of repeated measures (MMRM) model of the emraclidine groups and placebo group in the endpoint of interest.

5. Strategy for Intercurrent events (ICEs): A hypothetical strategy to address ICEs of potential death, treatment discontinuations, missed visits, and start of prohibited concomitant medications will be utilized. The data after the start of prohibited concomitant medications (ATC classifications of BUTYROPHENONE DERIVATIVES, INDOLE DERIVATIVES, and OTHER ANTIPSYCHOTICS) after the first dose of IMP and prior to the last dose of IMP with use duration of use of at least 4 days will be censored under the hypothetical strategy. The hypothetical strategy allows the study to assess the effect of emraclidine treatment without the confounding effect of prohibited concomitant treatments.

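### An antipsychotic restarted after the last dose with its start day missing can be imputed back onto treatment, and valid PANSS and CGI-S scores, including Week 6, can then be censored

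*SAP*

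**What the plan says.** **Date rule.** SAP 4.1.12 applies one algorithm to adverse events and to medications. For medications its stated purpose is to classify use as pre-dose, concomitant or post last dose. If the start day is missing and the month is that of IMP, the start becomes Day 1. In other cases: "Otherwise, the start day will be set to the first day of the month". With no year, "In the unlikely event of a completely missing start date (year not present), the start date will be imputed as Day 1". A missing end day becomes the last day of the month, and a fully missing end date not marked ongoing is treated as ongoing. The only bounds on an imputed date are the other date of the same event and the date of study withdrawal. The last dose of IMP is not a bound.

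**Censoring rule.** SAP 5.9.1 and 5.10.1 censor PANSS and CGI-S data after the start of an antipsychotic in one of three ATC classes (butyrophenone derivatives, indole derivatives, other antipsychotics), if it started "after the first dose of IMP and prior to the last dose of IMP with use duration of use of at least 4 days". Pattern 2b in SAP 5.9.3.2 uses the same definition for the MNAR cases. None of these sections says whether imputed dates count.

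**Post-trial use.** SAP 3.2.7 keeps later drugs apart: "Medications that start after the last dose of IMP will be classified as taken post last dose and will not be considered as concomitant". Protocol 6.6 expects completers who do not enter the extension to restart; they "will resume treatment with available antipsychotic medications at the discretion of and as determined by their physician". The Schedule of Assessments has medications recorded up to the last contact, a phone call or similar about 28 days after the last dose.

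**The concern.** A default that pushes an uncertain start towards treatment is cautious for deciding whether an adverse event is treatment-emergent. Applied to antipsychotics it works the other way: it can create an intercurrent event that never happened and delete observed efficacy data.

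Incomplete dates are also more likely off treatment than on it. Under Protocol 4.1.2, "Participants are to remain in the inpatient facility for the entire duration of the trial", up to Week 6 or early termination, so drugs given on treatment should be fully dated. A restart after discharge, reported by phone weeks later, is a likelier place for a missing day.

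At stake are Week 6 scores used in all four confirmatory tests (SAP 5.3 and 5.4). Active-arm participants flagged in this way would also have truly observed scores replaced by delta-shifted imputations in the tipping-point analysis (SAP 9.6.2). Since SAP 4.1.12 keeps imputed dates out of the listings, a reader could not see why a score had been dropped.

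**Working it through.** **1. The plan's own figures reproduce.** SAP 1.2 says 93 completers per arm "should provide at least 90% power to detect an effect size of 0.48".
- Required n per arm = 2(1.960 + 1.282)²/0.48² = 91.2, so 92 against 93 stated.
- Power at n = 93 is Φ(0.48·√(93/2) − 1.960) = Φ(1.313) = 90.5%.
- 93/0.75 = 124 per arm; 3 × 124 = 372. The completer total is 3 × 93 = 279.

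**2. Worked example.** First dose 6 April, so Day 42 = 17 May (Week 6 PANSS and CGI-S) and Day 45 = 20 May (last dose). A listed antipsychotic is restarted on 23 May and recorded as May, day unknown, ongoing.
- May is not the month of first dose, so the imputed start is 1 May = Day 26.
- Day 26 lies between first and last dose, and use lasts at least 4 days.
- The scores of Day 28 (3 May), Day 35 (10 May) and Day 42 (17 May) are censored, although all precede the real restart.

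**3. How often this happens, given such a record.** Inputs: PANSS on Day 42, last dose on Day 45, true restart on study day r > 45, start day missing, month known. A restart after Day 45 never falls in the month of Day 1, so the first-of-month branch applies if the month of IMP means the month of first dose. With day of the month m for the restart, the imputed study day is r − m + 1. The mean month length is 1461/48 = 30.44 days. Over all calendar start dates, approximately:
- dated before the last dose: 1 − (r − 44)/30.44
- Week 6 on or after the imputed start: 1 − (r − 42)/30.44
- Week 6 strictly after the imputed start: 1 − (r − 41)/30.44

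For r = 49 these give 84%, 77% and 74%. Direct enumeration over 1,461 consecutive start dates, with the restart day spread evenly over the interval, gives:

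| Restart after last dose | Dated on treatment | Week 6 lost (on or after) | Week 6 lost (strictly after) |
|---|---|---|---|
| 1-7 days | 84% | 77% | 74% |
| 1-14 days | 72% | 66% | 62% |
| 1-28 days | 49% | 43% | 39% |

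For restarts within 7 days that lose Week 6, between 1 and 4 weekly scores go (mean 2.2).

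**4. Possible number of scores.** The documents give no share of incomplete dates, so 2% to 5% of the 279 planned completers is an assumption.
- Low: 279 × 0.02 × 0.39 = 2.2
- High: 279 × 0.05 × 0.74 = 10.3

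The on-or-after count gives 2.4 and 10.7. No reduction has been made for participants who roll over or for drugs outside the three classes.

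**5. Effect on power.** As a worst case, treat each lost score as carrying no information. Power is 90.3% with 1% of scores lost, 90.0% with 2% and 89.1% with 5%. Ten of 279 is 3.6%.

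**The case against.** The strongest reply is that the link between the two rules is inferred. SAP 5.9.1 and 5.10.1 do not cite 4.1.12, whereas SAP 5.15.1 does so expressly for adverse event onset. That is fair, and the point is conditional on it. Still, a record dated only to the month of the last dose cannot be classified without some rule, and 4.1.12 is the only one given.

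Second, SAP 5.9.3.2 already has MNAR cases identified before lock and unblinding, in Section 9.5. The content of that section is not available here, so nothing is asserted about who is on the list. But the step uses the same timing definition and states no exception for imputed dates, so it is not shown to prevent the error.

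Third, exposure is limited. The eCRF asks for a start date (Protocol 6.7.1). Protocol 4.1.3 allows up to 7 inpatient days after the last dose for stabilization on other therapy, when starts should be well dated. Rollover participants have no follow-up contact. Only three ATC classes count. All of this stands and lowers the number.

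Stronger readings are tempting but unsupported:
- A reader might infer that post-trial restarts in general are censored. With a complete start date none is.
- A reader might apply the percentages to all 372 randomized. They are completer probabilities and belong with about 279.
- A reader might count starts imputed to Day 1 as censoring events. The rule needs a start after the first dose, and whether a date-only Day 1 start qualifies is unclear. The same uncertainty arises if the month of IMP means any dosing month, since May in the example would then go to Day 1.
- A reader might infer bias in a known direction. Those who restart may differ in response, but the documents show no direction.

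**Conclusion.** The point holds in conditional form. SAP 4.1.12 sets no floor at the last dose, so a restart after the trial with a missing day can be placed on treatment and remove genuine PANSS and CGI-S scores. It takes all of the following: an incomplete start date, one of the three ATC classes, at least 4 days of use, a month whose first day falls inside treatment and no later than the score, and a flag built from imputed dates. The end-date defaults make the duration condition easier to meet.

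The likely number is small: roughly 2 to 10 Week 6 scores under the assumed 2-5%, before further reductions, with power staying close to 90%. Early terminators have no scheduled Week 6 score to lose and are outside that count, though a validly timed early termination score could be censored by the same route. The reason to act is that a written rule can discard primary endpoint data for an event that did not occur on treatment, and this is cheap to prevent.

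**What to change.** 1. State in SAP 4.1.12, 5.9.1, 5.10.1 and 5.9.3.2 (2b) that the start and end date defaults designed for adverse events are not used to set the antipsychotic intercurrent-event flag or to pass the 4-day duration test.
2. Query every antipsychotic record with an incomplete date and adjudicate it against the inpatient source record, in the blinded pre-lock review that produces Section 9.5.
3. If a record stays unresolved and its known date parts allow a start after the last dose, do not impute the start to before the last dose in the main analysis. Treat it as on-treatment use in a sensitivity analysis.

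The cost is SAP wording before unblinding, some date queries and one sensitivity run. The downside is that a true on-treatment start with an incomplete date could be missed in the main analysis, leaving confounded scores in. This matters most for early terminators, whose partial date in the month of last dose may be real on-treatment use. That is why adjudication comes first and the sensitivity analysis takes the opposite assumption, in place of a blanket default to the day after the last dose.

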5.2 Exclusion Criteria

Individuals are not eligible for participation in this trial if any of the following criteria apply:

Target Disease	
1.	
Current DSM-5 diagnosis other than schizophrenia including, but not limited to, intellectual disability; schizoaffective disorder; major depressive disorder; schizopreniform disorder; psychotic depression; bipolar disorder; post-traumatic stress disorder; generalized anxiety disorder, obsessive compulsive disorder, eating disorders (bulimia, anorexia), or other anxiety disorders as a primary diagnosis (note: anxiety symptoms secondary to schizophrenia are allowed); delirium, dementia, amnestic, or other cognitive disorders.
 
Acute depressive symptoms within 30 days prior to signing the ICF that require treatment with an antidepressant are exclusory.
 
Acute manic symptoms within 30 days prior to signing the ICF that require treatment with a mood stabilizer are exclusory.
 
Additional excluded conditions include borderline, paranoid, histrionic, schizotypal, schizoid, or antisocial personality disorder.

2.	
Any of the following:
 
 • Schizophrenia considered resistant/refractory to antipsychotic treatment by history (failure to respond to 2 or more courses of adequate pharmacological treatment defined as an adequate dose per label and a treatment duration of at least 4 weeks) • History of response to clozapine treatment only or failure to respond to clozapine treatment for schizophrenia
3.	
Any of the following regarding history of schizophrenia:
 
 • Time from initial onset of schizophrenia <2 years based on prior records or participant self-report • Presenting with an initial diagnosis of schizophrenia • Presenting for the first time with an acute psychotic episode requiring treatment
4.	Reduction (improvement) in PANSS total score of $\geq 20\%$ between Screening and Baseline.
5.	
Either of the following:
 
 • History of tardive dyskinesia • Extrapyramidal symptoms that required medication within 6 months prior to signing the ICF
Other Medical History and Concurrent Conditions	

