### 1.1. Study Overview

This is a Phase 2, multicenter, randomized, double-blind, placebo-controlled, parallel-group, 6-week trial to evaluate the efficacy, safety, and tolerability of 2 fixed doses of emraclidine (15 mg once daily [QD] and 30 mg QD) in male and female subjects aged 18 to 65 years, inclusive, who have schizophrenia and are experiencing an acute exacerbation of psychosis. The trial will include up to a 15-day Screening Period (up to a maximum of 21 days allowed with approval of the medical monitor), a 45-day Inpatient Treatment Period, and a 28-day Follow-up Period. Each subject will participate in the trial for up to approximately 13 weeks.

Details of schedule of assessments are provided in [Section 9.1](#).

Approximately 600 subjects will be screened to achieve approximately 372 subjects qualified to be randomized to treatment in the trial.

In the event of higher than anticipated early terminations due to COVID-19 or other reasons, Cerevel may extend enrollment in order to achieve trial objectives.

[figure not shown]
On Day 1 (Baseline), subjects will be randomized in a 1:1:1 ratio to the following treatment groups with approximately 124 subjects per treatment group:

- Emraclidine 15 mg QD
- Emraclidine 30 mg QD
- Placebo QD

The randomization will be stratified by geographic region with 2 strata: United States or all other countries.

The daily dosing schedule will start on Day 1 with all subjects receiving a single, oral, daily dose of investigational medicinal product (IMP) in the morning. All subjects will continue dosing through Day 45 of Week 6.

The trial design is depicted in [Figure 1](#).

**Figure 1:** Trial Schematic

Abbreviations: QD=once daily; R=randomization.

Note: Assessment time points are planned for the last day of the indicated week (eg, Day 7, 14, 21, etc) with a  $\pm 2$  day window (see Schedule of Assessments in [Section 9.1](#)).

- Subjects will be admitted to the inpatient facility at the time they sign the ICF and remain in the inpatient facility for the duration of treatment.
- Extension of screening (up to a maximum of 21 days total) is allowed following discussion and documented approval by the medical monitor prior to the expiration of the Screening Period.

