#### 4.1.2. Day 1 (Baseline)

Day 1 is the day IMP is first initiated.

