## 5.6. Subject Disposition, Demographic and Baseline Characteristics

Subject disposition will be based on the ITT population with tabulation of the number of subjects who complete the study and the number of subjects discontinued from the study and the reasons by treatment group. Additionally, the number of days on study will be summarized.

Further tabulation by region (United States, Other Countries) and country will also be presented. Subject disposition data will also be tabulated for all subjects screened to include the number of subjects screened, the number of screen failures, and the reason for screen failure.

Number of subjects in each analysis population set will be summarized.

Additionally, the number of subjects randomized at each site and overall will be summarized by country, treatment group, and overall. Summaries will be presented for randomized subjects and completed subjects.

Demographic data and baseline characteristics including age, age group, sex, fertility status, race, ethnicity, smoking status (smoker vs. non-smoker) at Baseline, height at screening, weight at screening and baseline, BMI at screening and baseline, will be summarized using descriptive statistics for the ITT population. Further tabulation by region and country also will be presented.

Baseline disease characteristics including time (years) since diagnosis of schizophrenia, number of hospitalizations in the last 5 years, PANSS total score at Baseline, PANSS positive subscale score at Baseline, PANSS negative subscale score at Baseline, PANSS Marder Negative score at Baseline, PANSS delusions score at Baseline, PANSS conceptual disorganization score at Baseline, PANSS hallucinatory behavior score at Baseline, PANSS suspiciousness/persecution score at Baseline, CGI-S score at Baseline, change in PANSS total score from Screening to Baseline (Screening – Baseline), and percent change in PANSS total score from Screening to Baseline will be summarized by treatment group. Further tabulation by region and country also will be presented.

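### SAP 4.1.12 imputes a schizophrenia onset date with no year as Day 1, giving an impossible time since onset, and the SAP uses onset and diagnosis inconsistently

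*SAP*

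**What the plan says.** SAP 4.1.12 (Handling of Incomplete or Missing Dates) sets one algorithm for three kinds of date: adverse events, medications and non-drug therapies, and the onset of the disease. The third is named explicitly: "for date of initial onset of schizophrenia to determine time since onset". For a start date with no year, the rule is: "In the unlikely event of a completely missing start date (year not present), the start date will be imputed as Day 1". SAP 4.1.2 fixes the meaning of that day: "Day 1 is the day IMP is first initiated".

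The only illness-duration formula in the SAP is in 4.1.11: "Time (years) since diagnosis of schizophrenia is calculated as the difference in years from date of diagnosis to date of informed consent". The baseline table in SAP 5.6 uses the same variable: "Baseline disease characteristics including time (years) since diagnosis of schizophrenia". It is summarized by treatment group, with further tabulation by region and country.

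Protocol 5.2, exclusion criterion 3, excludes anyone with: "Time from initial onset of schizophrenia <2 years based on prior records or participant self-report". The same criterion excludes people presenting with an initial diagnosis or a first acute episode.

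**The concern.** For an adverse event or a medication, Day 1 is a sensible default when the date is unknown. It makes the event treatment-emergent or the drug concomitant, which is the cautious direction. For an illness that began years before the trial, the same default produces a value known to be false. It places the onset of schizophrenia after consent, on the day of first dosing.

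There is also a mismatch of terms. Section 4.1.12 imputes onset in order to obtain time since onset, but the SAP gives no formula for that quantity and lists it in no table. What is defined and tabulated is time since diagnosis, and 4.1.12 does not mention the diagnosis date. A programmer must therefore guess whether the imputed date enters the baseline table. At stake is one descriptive baseline variable, and in particular its minimum.

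**Working it through.** The plan states no figure to reproduce on this point, so the check is date arithmetic on the SAP's own rules.

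**Inputs**
- Imputed onset when the year is unknown: Day 1, the first dose (SAP 4.1.12, 4.1.2).
- Reference date in the only duration formula: informed consent (SAP 4.1.11).
- Consent to Day 1: at least 1 day, since the schedule runs screening from Day -15 to Day -1. The upper end comes from SAP 1.1: "The trial will include up to a 15-day Screening Period (up to a maximum of 21 days allowed with approval of the medical monitor").
- Minimum true time since onset in an eligible participant: 2 years (Protocol 5.2, exclusion 3).
- Planned arm size: 124 (SAP 1.1).

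**Step 1: the imputed duration.** Duration in years = (reference date - Day 1) / 365.25.
- Counted to Day 1: 0.
- Counted to consent, 1 day before: -1/365.25 = -0.003.
- Counted to consent, 15 days before: -15/365.25 = -0.041.
- Counted to consent, 21 days before: -21/365.25 = -0.057.

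All of these fall below the 2-year floor for onset.

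**Step 2: does another rule correct it?** Section 4.1.12 has two relevant overrides. One replaces an imputed start date that falls after the end date, but an ongoing illness has no end date. The other caps an imputed date at study withdrawal, which does not precede Day 1. Neither applies.

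**Step 3: do the partial-date rules share the fault?** They assign Day 1 only when the known month and year, or the known year, match those of dosing. An onset at least 2 years before consent cannot fall in the calendar year of dosing. An eligible onset date with a known year therefore goes to the first of the month or 1 January. Only the no-year rule gives an impossible onset.

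**Step 4: size, if the value reaches the baseline table.** With k imputed values x in an arm of N, and a mean of m among the others, the shift in the arm mean is k(x - m)/N. Take N = 124 and x = -0.041 years. The documents give no mean duration, so m = 5 to 20 years is an assumption.

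| Imputed cases in the arm | m = 5 years | m = 20 years | Relative shift |
|---|---|---|---|
| 1 | -0.04 | -0.16 | about -0.8% |
| 3 | -0.12 | -0.49 | about -2.4% |
| 6 | -0.24 | -0.97 | about -4.9% |

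For example, one case with m = 5 gives (-0.041 - 5)/124 = -0.041 years. The relative shift is close to k/N whatever the mean, so it would be larger in the region and country tables, where denominators are smaller. The minimum, which SAP 5.1 includes among the descriptive statistics, becomes zero or negative after a single case.

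**The case against.** The strongest reply is that the documents do not show the baseline table to be affected. The imputation concerns onset and the table reports time since diagnosis. The imputed date reaches the table only if the case report form holds one field for both, or if the rule is extended to diagnosis. The documents settle neither. This stands, so distortion of the table is conditional. The 2-year floor also applies to onset and not to diagnosis, although a zero or negative time since diagnosis would still be false for a participant who cannot be presenting with an initial diagnosis.

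The trigger should also be rare. Sites must establish that onset was at least 2 years ago, and the SAP itself expects a fully missing date to be unlikely. Self-report is accepted, however, and a participant can satisfy the criterion without giving a calendar year, so the case is not excluded. The median and quartiles would barely move with one such value.

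A reader might infer that imputed participants would appear to breach exclusion 3. The documents do not support this. Eligibility is judged at Screening and Baseline from records or self-report, SAP 4.1.12 keeps imputed dates out of the listings, and deviations are reviewed by the project team before unblinding (SAP 5.17). At most, an odd minimum would appear in a summary table.

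A reader might also object to the first-of-month and 1 January rules, since 1 January lengthens a year-only duration by about half a year on average if onsets are spread evenly over the year. That is a choice among conventions. It is pre-specified, is the same in every arm and produces no impossible value.

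**Conclusion.** The no-year rule is wrong as written for the date of initial onset. It yields 0 or -0.003 to -0.057 years where eligibility requires at least 2 years, and no other rule corrects it. The terms are also inconsistent: 4.1.12 serves time since onset, while 4.1.11 and 5.6 define and tabulate time since diagnosis.

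The stronger statement, that the baseline disease table is distorted, cannot be made from the documents. It holds only if the imputed date feeds the tabulated duration. In that event one case in an arm of 124 makes the minimum zero or negative and lowers the mean by about 0.8%, or 0.04 to 0.16 years under the assumed mean of 5 to 20 years. How many cases to expect is unknown.

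This is a minor descriptive point. Illness duration is not a covariate (SAP 5.5, 5.9.2), a subgroup (5.9.4), an estimand attribute (5.9.1) or an input to the missing-data analyses (5.9.3.2). No efficacy result depends on it.

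**What to change.** In SAP 4.1.12, exclude the schizophrenia onset/diagnosis date from the Day 1 default. When the year is unknown, leave the duration missing and report the number missing in the baseline table. Choose one term, onset or diagnosis, and use it in 4.1.11, 4.1.12 and 5.6, so that the date imputed, the formula and the tabulated variable are the same quantity. If both are wanted, each needs its own definition. The first-of-month and 1 January rules for partial dates may stay.

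The cost is about two sentences in the SAP and a missing count in one table. No data collection, sample size or efficacy analysis changes.
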